APPENDIX II

Г

1HP Medication Diary ARM A						
PID	(sticker)		Month			
ose #	Date of dose	Time of dose	Food and drink taken with HP	Initials		
example	1 Jan 2020	7:30 am	Rice, beans, 1 egg, coffee with milk	lnot		
1						
2						
 						
5						
6						
7						
8						
9						
10						
11						
12						
13						
14						
15						
17						
18						
19						
20						
21						
22						
23						
24						
25						
20						
27						
20 Notes:			1			
110165.						

3HP Medication Diary
ARM B

PID	_(sticker)			
Dose #	Date of dose	Time of dose	Food and drink taken with HP	Initials
example	1 Jan 2020	7:30 am	Rice, beans, 1 egg, coffee with milk	lnot
1				
2				
 				
5				
6				
7				
8				
9				
10				
11				
12				
Notes:				

Participants will need a dosing source document for their home TPT doses.

Print medication diary on heavy card stock. Fold, staple, or tape a blank cover on top to keep the record private.

Distribute the card with the first TPT dose. Ask/remind participants to bring the card to every visit.

Have the participant fill the card during the first TPT DOT dose in clinic as practice for when s/he will fill the card for home doses.

APPENDIX III

Hypersensitivity Symptom Checklist

```
Date HP Given: ____/___/
```

Dose #: _____

Time: ____h____

1. Any symptom/ sign to be followed by a comment and reported to the Investigator on duty who will complete a Hypersensitivity Checklist form

2. Any event recorded on this form MUST also be recorded on the Adverse Event Log

Date	Time	Medical event	Tick if	Initial and
			Present	Comment
		Hypotension		
		Urticaria (Hives)		
		Angioedema		
		(swelling around lips/ eyes)		
		Acute bronchospasm		
		Conjunctivitis (Red, itchy eyes)		
		Thrombocytopenia		
		Neutropenia		
		Anaphylaxis		
		Flu-like syndrome:		
		Weakness		
		Fatigue		
		Muscle Pain		
		Nausea		
		Vomiting		
		Headache		
		Fever/ Chills		
		Body Aches		
		Rash		
		Itching		
		Sweats		
		Dizziness		
		Shortness of breath		
		Chest pain		
		Cough		
		Syncope		
		Palpitations		

APPENDIX IV

List of Precautionary Medications

Precautionary Agents with INH

Carbamazepine Chlorzoxazone Disulfiram Ketoconazole Phenytoin Warfarin Theophylline Selective serotonin re-uptake inhibitor antidepressants (e.g. citalopram, fluoxetine, paroxetine, sertraline)

Medication Class	Precautionary Medications
Antiarrhythmics	Disopyramide
	Mexiletine
	Quinidine
	Tocainide
Antibiotics	Chloramphenicol
	Clarithromycin
	Dapsone
	Doxycycline
	Fluoroquinolones
Anticoagulants	Warfarin
Anticonvulsants	Phenytoin
Antimalarials	Quinine
Antipsychotics	Haloperidol
	Fluconazole
Azole Antifungals	Itraconazole
5	Ketoconazole

Precautionary Agents with RPT

Medication Class	Precautionary Medications					
Barbiturates	Phenobarbital					
Benzodiazepines	Diazepam					
Beta-Blockers	Propranolol					
	Diltiazem					
Calcium Channel Blockers	Nifedipine					
	Verapamil					
Cardiac Glycoside Preparations	Digoxin					
Corticosteroids	Prednisone					
Fibrates	Clofibrate					
Oral hypoglycemic agents	Sulfonylureas					
Hormonal	Ethinyl estradiol					
Contraceptives/ Progestins	Levonorgestrel					
-	Cyclosporine					
Immunosuppressants	Tacrolimus					
Methylxanthines	Theophylline					
Narcotic analgesics	Methadone					
Phosphodiesterase-5 (PDE-5) Inhibitors	Sildenafil					
Thyroid preparations	Levothyroxine					
	Amitriptyline					
Tricyclic Antidepressants	Nortriptyline					

APPENDIX V DAIDS Grading Table v 2.1 https://rsc.niaid.nih.gov/sites/default/files/daidsgradingcorrectedv21.pdf

1. INTRODUCTION

This document contains the statistical analysis plan for the Ultra Curto TPT study. The goal is to avoid data-driven analyses during and at the end of the study to the extent possible. Much of the content of this Statistical Analysis Plan (SAP) is taken directly from the Ultra Curto TPT Study Protocol, version 3.1 of 24 November 2021.

2. BACKGROUND

2.1. Study Overview

This multi-center study compares the treatment success and safety of 3 months of weekly rifapentine and isoniazid (3HP) to one month of daily rifapentine and isoniazid (1HP) in HIV-uninfected adolescents and adults.

3. OBJECTIVES and HYPOTHESES

3.1 Primary Objectives

To compare treatment success of 1HP with 3HP in HIV-uninfected adults and adolescents at increased risk of TB.

To compare the safety of 1HP with 3HP in HIV-uninfected adults and adolescents at increased risk of TB.

3.2 Primary Outcomes and Hypotheses

(1) Treatment success of TBT with \geq 90% adherence documented by self-report, pill count, and pharmacologic monitoring.

Hypothesis: Successful treatment with 1HP will be superior to 3HP, with 90% of individuals randomized to 1HP taking >90% of prescribed doses vs 80% of those on 3HP.

(2) Safety of treatment regimens, defined as occurrence of Grade 2 or higher targeted safety events and discontinuation of study medications because of side effects. Targeted safety events are hypersensitivity syndrome, rash, peripheral neuropathy, hepatotoxicity, nausea and vomiting, and drug-related fever.

Hypothesis: We hypothesize that the safety of 1HP will be superior to 3HP, with a rate of targeted adverse events or medication discontinuation of 6% vs. 13% for 3HP.

3.3 Secondary Outcome and Hypothesis

(1) Incremental cost-effectiveness of 1HP and 3HP (compared to each other, 6H, and no treatment) using a societal perspective.

(2) Analyze, in each of the health units in the study, the time needed to provide comprehensive care to patients.

Hypothesis: We hypothesize that 1HP will be cost saving vs 3HP, vs modelled costs of 6H and vs no TPT.

3.4 Exploratory Aims

Incidence of active tuberculosis will be assessed during the six months following enrollment.

4. STUDY DESIGN

This is a multicenter, randomized, controlled, open-label, phase IV clinical trial with two arms, comparing treatment success and safety of 1HP vs 3HP in HIV-uninfected adolescents and adults.

4.1 Study Groups

TB preventive treatment:

Arm A (n=250): Experimental arm. Rifapentine 600 mg daily and isoniazid 300 mg daily for 4 weeks.

Arm B (n=250): Control arm. Rifapentine 900 mg weekly and isoniazid 900 mg weekly for 12 weeks.

[figure not shown]
Patient Population:

The study will enroll HIV-uninfected individuals who are ≥ 15 years old, and are candidates to receive TB preventive therapy (i.e. LTBI with no evidence of active TB). Key exclusion criteria include HIV infection, abnormal liver enzymes, neutropenia, previous treatment of TB or latent TB infection, or a history of study drug intolerance.

Study sites:

- Health units from Rio de Janeiro Health Secretariat and NAPDOT study clinic, Rio de Janeiro, Brazil
- Fundação de Medicina Tropical (FMT) [name] Dourado; Manaus, Amazonas State, Brazil

Figure 1. Study Schema

5. RANDOMIZATION

The Stata randomization code was run and saved in a file by [name], stratified by the two sites, with randomly permuted blocks of several random block sizes (details not given here for reasons of masking security). Eligible patients who meet all of the inclusion criteria and none of the exclusion criteria will be randomized in a 1:1 ratio to the study arms. Contacts of the same index case will be considered a cluster and assigned to the same treatment arm according to the randomization of the first enrolled contact. Cluster (contacts of an index patient) size is limited to 2 participants per index case due to the diminishing returns in terms of power per enrollee within a household.

Randomization will be stratified by study site. After household contacts have signed informed consent forms, they will be randomized as a cluster to the same study arm, i.e. all receiving the same regimen. Other household members subsequently identified will not be eligible for the study.

The study is unblinded for practical reasons owing to differing pill counts between the arms and adherence being essential to the primary outcome.

6. SAMPLE SIZE CONSIDERATIONS

The sample size target is 500 evaluable adolescents and adults. Having each participant complete all of the scheduled drug sampling evaluations will provide approximately 1000 rifapentine and isoniazid pharmacological data points.

Assumptions, Outcome 1:

Successful treatment with 3HP = 80%

In clinical trials, reported completion rates of 3HP have ranged from 84-92% with directly observed therapy. In the CDC-sponsored iAdhere Trial, completion of self-administered 3HP was only 74-76%. In this study, which will use self-administered treatment, we estimate a completion rate of 80%. (Belknap 2017)

Successful treatment with 1HP = 90%

Completion of self-administered 1HP was 97% in the BRIEF TB Study, which was undertaken at research clinics in the ACTG and IMPAACT networks. We estimate that in a more real-world setting adherence will be slightly lower, but should still be at least 90%. We believe that demonstrating \geq 90% completion for 1HP, significantly greater than with 3HP, will provide compelling evidence for clinical practice and treatment guidelines to change.

Based on these assumptions, with an average cluster (household contacts of the index case) size of nearly 2, and an outcome coefficient of variation (CV) of 0.15, near the mean bound using the maximum entropy distribution (Chatfield 2020), a sample size of 250 individuals per arm, 500 total, would provide 80% power for detecting a significant difference at a two-sided 0.05 significance level. The sample size is not inflated for losses to follow up, as those who fail to complete the protocol will have reached a study endpoint.

Assumptions, Outcome 2:

Proportion of participants experiencing Grade 2 or higher targeted safety events with 3HP = 13%.

In TBTC Study 26 and the iAdhere Study, rates of drug-related adverse events with 3HP were 7-8%. In clinical cohort studies, rates of discontinuation for adverse events have been higher. An analysis of patients taking 3HP in

Taiwan found that treatment discontinuation due to adverse events occurred in 12%. (Chan, ERJ 2018) A study of health care workers in South Korea reported that 19% of those receiving 3HP had hypersensitivity reactions and 15% discontinued 3HP due to drug reactions. (Jo 2019) We conservatively assume the rate will be 13%.

Proportion of participants experiencing Grade 2 or higher targeted safety events with 1HP = 6%.

In the BRIEF TB trial the rate of targeted safety events was 3%. We would want to demonstrate a reduction from 13% to at least as low as 6% in HIV-negative patients. With a CV of 0.1 (again, in reference to the maximum entropy distribution for the corresponding proportions, which are lower here than for the previous outcome), and the sample size of 250 individuals (about 125 households) in each study arm, we will have about 80% power for detecting a significant difference at a two-sided 0.05 significance level. We would also have 80% power to distinguish between risks of 12% and 5% in the two study arms. Although for convenience we have phrased this in terms of an hypothesis test, our goal is to estimate the difference in safety risks. With this sample size, and risks of 13% and 6% with 3HP and 1HP, respectively, the 95% CI for the risk difference will have a half-width of 3 percentage points. Reporting this CI will enable readers to make their own conclusions regarding non-inferiority of 1HP with respect to 3HP, in addition to superiority. (Dunn 2018)

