15.8.3 Analysis Plan

Analyses will be intention-to-treat for both primary outcomes of successful completion and safety. For the successful completion outcome, losses to follow up (at 4 weeks for Arm 1HP and 12 weeks for Arm 3HP) will be considered as unsuccessful; a sensitivity analysis will be conducted among those not lost in both arms as of 12 weeks. For the safety outcome as of 24 weeks, losses will be considered as failures (safety events).

For the primary outcomes, if fewer than 5% of failures occur in households with 2 or more failures, p-values will be calculated using Fisher's exact test, and 95% confidence intervals (CI) for risk differences will be calculated using the standard asymptotic formula.

Otherwise, within-household correlation will be accounted for using

generalized estimating equations with logit link (for p-value) or identity link (for risk difference CI) and exchangeable correlation structure. If there are convergence problems, a log link function will be used, with delta-method-constructed confidence intervals.

Incidence of active tuberculosis will only be assessed during six months following enrollment but will be evaluated as an exploratory outcome. Incidence will be compared using Kaplan-Meier estimates at 24 weeks and Greenwood's variance formula. This will be a sufficiently rare event that within-household correlation will be ignorable. Censoring will be at last study visit or death. As a sensitivity analysis, TB-free survival will also be analyzed.

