10.2 Outcome Definitions

10.2.1 Treatment completion and successful treatment

1HP

Completion of therapy is defined as having completed 28 daily doses of treatment within 6 weeks. Treatment success is defined as having taken at least 25 doses of medication confirmed by patient report and pill count, and having rifapentine or isoniazid detected at least once in urine or DBS specimens.

3HP

Completion of therapy is defined as having completed at least 12 weekly doses of treatment within 18 weeks. Treatment success is defined as having taken at least 11 doses of medication confirmed by patient report and pill count, and having rifapentine or isoniazid detected at least once in urine or DBS specimens.

Figure 2 shows the algorithm that will be used to classify patients as having treatment success of failure. This hierarchical approach begins with self-reported adherence, then uses pill count, and finally a composite of test results for isoniazid in urine and rifapentine and des-RPT in DBS.

[figure not shown]

Figure 2 Treatment Success

For the treatment success outcome, note that when loss to follow up precludes being able to demonstrate the requisite number of doses having been taken, the outcome is classified as "unsuccessful." A sensitivity analysis will be conducted among those who complete their last scheduled visit after 23 weeks on study.

10.2.2 Safety: Numbers of participants with at least one occurrence of Grade 2 or higher targeted safety events and/or discontinuation of study medications because of side effects attributed to study medications.

Targeted safety events are hypersensitivity syndrome, rash, peripheral neuropathy, hepatotoxicity, nausea and vomiting, and drug-related fever.

This study will grade toxicity and adverse events according to the *Division of AIDS (DAIDS) Table for Grading Adult and Pediatric Adverse Events, Corrected Version 2.1* (dated July 2017).

https://rsc.niaid.nih.gov/sites/default/files/daidsgradingcorrectedv21.pdf See Appendix V of the study protocol.

For the primary safety outcome as of 24 weeks, those who do not complete their last scheduled visit after 23 weeks on study will be considered as failures (safety events).

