10.3.1 Treatment Success and Safety

A superiority framework will be used for these analyses, with statistical significance defined as p<0.05 for each of the two primary outcomes. No multiplicity correction will be employed.

For each of the primary outcomes, if fewer than 5% of failures (unsuccessful treatment; specified Grade 2 event) occur in households with 2 or more failures, p-values will be calculated using Fisher's exact test, and 95% confidence intervals (CI) for risk differences will be calculated using the standard asymptotic formula.

Otherwise, within-household correlation will be accounted for using generalized estimating equations with logit link (for p-value) or identity link (for risk difference CI) and exchangeable correlation structure. If there are convergence problems with the risk difference estimation, a log link function will be used, with delta-method-constructed confidence intervals for risk differences.

Subgroup analyses will be performed by:

Site Sex Age (dichotomized at overall median) Weight (dichotomized at overall median)

Interaction tests will assess differential effects.

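### The safety sizing allows for no losses, but the analysis counts every loss as a safety event in either arm, so the stated power of about 80% is for a different endpoint

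*SAP*

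**What the plan says.** **Sizing.** SAP section 6 and protocol 15.4 give two sets of assumptions. The Outcome 1 (treatment success) text ends: "The sample size is not inflated for losses to follow up, as those who fail to complete the protocol will have reached a study endpoint". The Outcome 2 (safety) text follows with its own inputs: "Proportion of participants experiencing Grade 2 or higher targeted safety events with 3HP = 13" per cent and "Proportion of participants experiencing Grade 2 or higher targeted safety events with 1HP = 6" per cent. With "the sample size of 250 individuals (about 125 households) in each study arm" and a CV of 0.1, it concludes that "we will have about 80% power for detecting a significant difference at a two-sided 0.05 significance level". It adds that 12% v 5% would also have 80% power. It mentions no losses.

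**Analysis.** SAP 10.2.2 states that "those who do not complete their last scheduled visit after 23 weeks on study will be considered as failures (safety events". Protocol 15.8.3 has the same rule: "For the safety outcome as of 24 weeks, losses will be considered as failures (safety events". Neither document limits it to one arm. SAP 10.3.1 tests each primary outcome for superiority at p<0.05 and states: "No multiplicity correction will be employed".

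**Sensitivity to loss.** Both documents specify a sensitivity analysis for losses in treatment success. Neither specifies one for safety.

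**The concern.** For treatment success, a lost participant is a failure, and the assumed 80% and 90% can be read as already net of such failures. For safety, the 13% and 6% are supported by rates of drug-related adverse events, discontinuation for adverse events, hypersensitivity reactions and targeted safety events. Nothing cited for them includes losses. Scoring losses as events then adds non-drug events to both arms. The denominator stays at 250 per arm, but the difference shrinks and the variance grows.

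The stated power therefore holds only if nobody is lost over 24 weeks. A non-significant safety result could be read as similar toxicity when part of the cause is retention. If loss differs between the arms, the safety difference itself partly measures retention.

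**Working it through.** **Inputs from the documents:** 13% (3HP) and 6% (1HP); 250 per arm in about 125 households; two-sided 0.05; CV 0.1; losses scored as events. **Assumptions not in the documents:** the loss rate L, equal loss in both arms, and loss independent of events.

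**Formulas.** With analysed rates r3 and r1 and n = 250:
- SE = √{[r3(1−r3) + r1(1−r1)]/n}
- unpooled power = Φ(|r3−r1|/SE − 1.96)
- pooled power = Φ{[|r3−r1|√n − 1.96√(2p̄(1−p̄))]/√[r3(1−r3) + r1(1−r1)]}, where p̄ is the mean of r3 and r1

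**Step 1: the plan's own figures, no loss.**
- 13% v 6%: SE = √[(0.1131 + 0.0564)/250] = 0.02604 and 0.07/0.02604 = 2.688. Power is 76.7% unpooled and 76.2% pooled, about 4 points under the stated 80%. That shortfall is a separate matter.
- 12% v 5%: 80.7% unpooled and 80.3% pooled, which matches the stated 80%.
- Outcome 1 also reproduces: 80% v 90% at CV 0.15 gives 80.1% by the Hayes–Bennett cluster formula.

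**Step 2: rates under the loss rule.** r = L + (1−L)p.
- L = 5%: 0.05 + 0.95×0.13 = 17.35% and 0.05 + 0.95×0.06 = 10.70%; difference 6.65 points.
- L = 10%: 0.10 + 0.90×0.13 = 21.70% and 0.10 + 0.90×0.06 = 15.40%; difference 6.30 points.

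**Step 3: power at those rates.** At L = 5%, SE = 0.03092, 0.0665/0.03092 = 2.151 and Φ(0.191) = 57.6%. At L = 10%, SE = 0.03465, 0.0630/0.03465 = 1.818 and Φ(−0.142) = 44.4%.

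| Loss in each arm | Analysed rates | Power (pooled to unpooled) |
|---|---|---|
| 0% | 13.00% v 6.00% | 76.2–76.7% |
| 2% | 14.74% v 7.88% | 67.9–68.3% |
| 5% | 17.35% v 10.70% | 57.2–57.6% |
| 10% | 21.70% v 15.40% | 44.1–44.4% |
| 15% | 26.05% v 20.10% | 35.1–35.3% |

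On the pooled formula, successive 5% steps cost 19.0, 13.1 and 9.0 points. Power reaches 50% at about 7.6% loss (unpooled). Fisher's exact test, which SAP 10.3.1 uses when failures cluster little, gives 72.7% with no loss and 52.9% at 5%. For 12% v 5%, power is 80–81% with no loss, 60% at 5% and 46% at 10%.

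**Step 4: relaxing the assumptions.**
- *Losses fall only on event-free participants.* At 5%, the rates are 18% v 11% and pooled power is 60.4%, a cost of about 16 points.
- *More loss on 3HP (7% v 3%).* Rates are 0.07 + 0.93×0.13 = 19.09% and 0.03 + 0.97×0.06 = 8.82%. The apparent difference is 10.27 points and power about 91%.
- *More loss on 1HP (3% v 7%).* Rates are 0.03 + 0.97×0.13 = 15.61% and 0.07 + 0.93×0.06 = 12.58%. The apparent difference is 3.03 points and power about 16%.

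**Step 5: household correlation.** Applied to 13% and 6%, CV 0.1 implies ICC = CV²p/(1−p): 0.01×0.13/0.87 = 0.0015 and 0.01×0.06/0.94 = 0.0006. The Hayes–Bennett formula then gives 76.2%, 57.1% and 43.9% at 0%, 5% and 10% loss, essentially unchanged.

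**The case against.** - **The no-inflation sentence belongs to Outcome 1.** This stands. The sentence precedes the Outcome 2 heading in both documents and is correct where it is. A reader might infer that the plan gives a false justification for safety. It gives none, so the defect is an omission in the Outcome 2 text.
- **Loss may be small.** Protocol 10.3 describes locator checks, reminder calls and home visits, and participants who stop treatment stay in follow-up. That may keep L low, but the documents do not state it, and even 2% loss takes about 8 points.
- **The aim is estimation.** SAP section 6 says so. But SAP 10.3.1 still sets a superiority test at p<0.05, and the rule also shrinks the estimated difference, from 7 points to 6.65 at 5% loss.
- **The target is 500 evaluable participants.** This does not help. SAP section 7 analyses all enrollees, and SAP section 8 uses a slightly modified intention-to-treat approach. Lost participants are counted, not replaced.
- **The 13% and 6% might already include losses.** The hypothesis in SAP 3.2 mentions medication discontinuation without qualification. However, the outcome definition just above it limits this to side effects, and no cited rate includes losses.
- **Equal, independent loss is the reviewer's assumption.** This stands. The power table is a range under that assumption, and step 4 shows how far unequal loss can move it.

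**Conclusion.** The mismatch is real. The stated safety power is for 13% v 6%, and the planned analysis compares rates that include losses. Under equal loss independent of events, power is about 76–77% with no loss, 57–58% at 5% and 44% at 10%. The documents supply no loss rate, so no single value can be called the trial's power.

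Four stronger readings are not supported:
- *Every 5% lost costs 19 points.* Only the first 5% does; later steps cost less.
- *A true halving of toxicity would probably be missed.* Under these assumptions that holds only above about 7.6% loss in each arm, and nothing in the documents says loss will reach that level.
- *Household correlation makes power much lower still.* That requires putting the CV of 0.1 on the event-free proportions. SAP section 6 ties it to proportions lower than those of Outcome 1, which fits 13% and 6%, and there the effect is negligible.
- *The losses-as-events rule must be dropped as the primary analysis.* It is pre-specified and consistent across both documents. Replacing it is debatable and is not needed to correct the sizing.

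**What to change.** In SAP section 6 and protocol 15.4:
1. Say that the no-inflation reasoning applies to Outcome 1 only.
2. For Outcome 2, state an assumed loss rate and restate the power at the rates the analysis will compare. With equal loss, examples are about 57–58% at 5% and 44% at 10%. Keep N at 500.

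In SAP 10.2.2 and protocol 15.8.3:

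3. Add a safety sensitivity analysis on observed targeted events and drug-related discontinuations that does not count losses as events.

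The cost is a few sentences, a less favourable stated safety power and one extra analysis. No more participants and no new data are needed.

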15.8.1 Planned Interim Analysis and Stopping Guidelines

After 25 participants in Arm A have completed 4 weeks treatment (28th HP dose), and 25 participants from ARM B have completed 4 weeks treatment (their 4th HP dose), we will conduct an interim safety and adherence assessment to ensure that 1HP is safe and well tolerated by HIV-negative participants, as compared with 3HP.

No early stopping rules will be formally adopted for this Phase IV trial.

Enrollment will not pause during the interim analysis. However, when participants from 80 households have completed 16 weeks on-study, a masked assessment of the within-household correlation will be made to verify sample size assumptions.

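### Power for the primary safety outcome (13% v 6%) is about 76–77% before any household correlation, not about 80%, and the CV of 0.1 behind it has no stated scale

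*SAP*

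**What the plan says.** SAP section 6 and protocol section 15.4 carry the same text. For outcome 2 the assumed risks are 13% on 3HP and 6% on 1HP, with "the sample size of 250 individuals (about 125 households) in each study arm" and a CV of 0.1. The plan concludes: "we will have about 80% power for detecting a significant difference at a two-sided 0.05 significance level". It adds: "We would also have 80% power to distinguish between risks of 12% and 5% in the two study arms". The CV is justified "in reference to the maximum entropy distribution for the corresponding proportions, which are lower here than for the previous outcome". For outcome 1 (80% v 90%) the CV is 0.15 and the stated power is 80%.

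Neither document names a sample-size formula or says whether the CV of 0.1 belongs to the proportion with an event or the proportion without one. Protocol section 15.8.1 provides that, once participants from 80 households have completed 16 weeks, "a masked assessment of the within-household correlation will be made to verify sample size assumptions".

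**The concern.** The two safety scenarios share the same sample size, CV and 7-point difference. The binomial variance is larger at 13% and 6% than at 12% and 5%, so power must be lower for the first pair. If 12% v 5% sits at 80%, 13% v 6% cannot. Yet 13% v 6% is the stated co-primary hypothesis.

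The CV is a second difficulty. A value of 0.1 means very different amounts of household correlation depending on whether it is applied to 13% and 6% or to 87% and 94%. Readers cannot tell how much clustering was allowed for, and the later masked check of the correlation has no clear value to verify.

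**Working it through.** **Inputs** (SAP section 6): risks 13% and 6%; 125 households of two per arm; CV k = 0.1; two-sided alpha 0.05. Calibration cases: 80% v 90% with k = 0.15, and 12% v 5% with k = 0.1.

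**1. Find a formula that reproduces the plan's other figures.** The usual cluster formula with c households of size m per arm is

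V = p0(1−p0)/m + p1(1−p1)/m + k²(p0² + p1²)

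c = 1 + (1.96 + 0.8416)² × V/(p0−p1)²

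power = Φ(√[(c−1)(p0−p1)²/V] − 1.96)

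| Scenario | V | Households per arm for 80% | Power at 125 | Stated |
|---|---|---|---|---|
| 80% v 90%, k = 0.15 | 0.1576 | 124.7 | 80.1% | 80% |
| 12% v 5%, k = 0.1 | 0.0767 | 123.9 | 80.4% | 80% |
| 13% v 6%, k = 0.1 | 0.0850 | 137.1 | 76.2% | about 80% |

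The first two reproduce and the third does not. For the third, V = 0.05655 + 0.02820 + 0.000205 = 0.084955. The CV term is about 0.2% of the total, so clustering plays almost no part. The requirement is 137.1 households, about 274 people per arm.

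**2. Ignore households altogether.** With 250 independent people per arm:

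- unpooled: SE = √[(0.1131 + 0.0564)/250] = 0.02604; 0.07/0.02604 − 1.96 = 0.728; power 76.7%
- pooled: (0.07 − 1.96 × 0.02623)/0.02604 = 0.714; power 76.2%
- arcsine: 77.5%, the highest two-sided result found
- Fisher's exact test, one of the two tests in SAP section 10.3.1: 72.7%

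Keeping 13% on 3HP and solving for the 1HP risk that gives 80% yields 5.7% (pooled and cluster formulas) to 5.75% (unpooled).

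**3. What a CV of 0.1 means on each scale.** With between-household SD equal to kp, ICC = k²p/(1−p).

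- Event scale: 0.01 × 0.13/0.87 = 0.0015 and 0.01 × 0.06/0.94 = 0.0006.
- Event-free scale: 0.01 × 0.87/0.13 = 0.067 and 0.01 × 0.94/0.06 = 0.157.
- For comparison, outcome 1 with CV 0.15: 0.0225 × 0.8/0.2 = 0.09 and 0.0225 × 0.9/0.1 = 0.20.

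**4. Compare with a maximum-entropy distribution.** I assume this is the maximum-entropy distribution on 0–1 with a given mean, which is a truncated exponential. Solved numerically, its CV is 0.99 at a mean of 13% and 1.00 at 6%. At the complements it is 0.148 at 87% and 0.064 at 94%, mean 0.106. So 0.1 fits the event-free scale and is far from the event scale. Outcome 1 shows the same pattern: 0.234 at 80% and 0.111 at 90%, mean 0.172, against the 0.15 used.

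**5. Power with household correlation.** For pairs the variance inflation in each arm is 1 + ICC.

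| Correlation for 13% v 6% | ICCs | Overall design effect | Power by design effect (pooled) | Simulated |
|---|---|---|---|---|
| CV 0.1, event-free scale | 0.067, 0.157 | 1.097 | 72.3% | 71.5–73.5% |
| Maximum-entropy CVs (0.99, 1.00) | 0.146, 0.064 | 1.119 | 71.5% | 72.7–73.3% |

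The first design effect is (0.1131 × 1.067 + 0.0564 × 1.157)/0.1695. The simulations used 200,000 trials of 125 pairs per arm with robust-variance tests; the range covers the logit and risk-difference scales.

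For 12% v 5% the same two assumptions give ICCs of 0.073 and 0.190, or 0.135 and 0.053. The design effect is about 1.11 in both cases and power is 76–77%, against 80.3–80.7% (pooled, unpooled) without correlation.

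**The case against.** The plan hedges the figure with the word about, the gap before correlation is only 3 to 4 points, and a 1HP risk of about 5.7% instead of 6% closes it. SAP section 6 also says that the aim is to estimate the difference and that the test wording is for convenience. All this limits the consequence. It does not make the figure right: the same paragraph gives an unhedged and accurate 80% for 12% v 5%, and SAP section 10.3.1 tests each primary outcome for superiority at p<0.05.

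The scale of the CV is an inference. The documents do not state it, and the cited paper was not available for this check. If the planners worked on the event-free scale, 0.1 is a reasonable value, and their remark about lower proportions makes sense for failure proportions (13% and 6%, against 20% and 10% for outcome 1). What stands is that the scale is unlabelled, not that the CV is shown to be wrong.

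Three stronger readings are tempting and unsupported:

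- Putting the larger correlation into the formula of step 1 gives 67–69%. For pairs that formula adds the whole between-household variance where only half belongs, and the documents never name it. The design-effect and simulated values of 71–73% are the ones to use.
- A reader might infer that the masked check will be judged against a CV ten times too small. Protocol section 15.8.1 gives no numerical benchmark, so this cannot be said.
- A reader might conclude that the sample size must rise. Nothing here requires that.

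**Conclusion.** The point holds. Power for 13% v 6% is about 76–77% with negligible household correlation, so the chance of missing the hypothesised safety gain is about 23–24%, not 20%. With household ICCs of 0.06–0.16 power is about 71–73%, a miss risk of about 27–29%. The first statement is firm: it uses only the plan's own inputs, and no two-sided method tried exceeds 77.5%. The second rests on reading the CV on the event-free scale, or on the truncated-exponential reading of maximum entropy. Both statements assume full pairs, whereas the plan says nearly 2 per household. Both also take the event risks as given, although SAP section 10.2.2 counts participants without a final visit as safety events, which would alter them. The outcome 1 power claim is not in question.

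**What to change.** In SAP section 6 and protocol section 15.4, with the sample size unchanged:

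- State that power for 13% v 6% with 125 households of two per arm is about 76% with negligible household correlation and about 71–73% with ICCs of 0.06–0.16, and that 80% power at a 13% control risk corresponds to a 1HP risk of about 5.7% without correlation.
- State that power for 12% v 5% is about 80% without correlation and about 77% with it.
- Give the assumed household variation as an ICC, or say whether the CV refers to event or event-free proportions, and name the formula used. Refer to that value in protocol section 15.8.1 so that the masked assessment has a defined reference.

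The cost is a few sentences in two documents and a less favourable stated power. No participants, visits or analyses change.
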